15.5 Secondary Objectives

Please refer to Section 8 for the secondary objectives and endpoints. The key secondary objective is to assess whether malignant glioma patients receiving RT and concomitant TMZ are more satisfied with rolapitant plus ondansetron vs. ondansetron for the prevention of RINV. Other secondary objectives include: (1) To describe

the rationale behind a patient's satisfaction with antiemetic preference based upon effectiveness, convenience, and global satisfaction, (2) To evaluate patient compliance with rolapitant plus ondansetron and ondansetron alone, and (3) To assess the safety of rolapitant plus ondansetron in the prevention of RINV in primary glioma patients receiving RT and concomitant TMZ.

15.5.1 Key Secondary Objective

The percentage of patients who prefer rolapitant plus ondansetron over ondansetron, as determined by response to the question with "Which nausea medication regimen was I most satisfied with?" will be calculated, with a 95% confidence interval. An exact binomial test assessing whether the proportion preferring the treatment regimen that includes rolapitant is 0.5 will be conducted. Logistic regression will explore the potential that sequence influences patient preference.

15.5.2 Other Secondary Objectives

Mean patient satisfaction scores for effectiveness, convenience and global satisfaction, will be computed based upon responses to the TSQM-9 treatment satisfaction survey¹⁶ that patients complete at the end of week 3 after treatment with ondansetron alone or combination treatment. Three subscales will be computed: effectiveness (3 items), convenience (3 items), and global satisfaction (3 items). Assuming there is no evidence of a carry-over effect, a paired t-test will be conducted comparing satisfaction with combination treatment and with ondansetron treatment alone.

The efficacy of rolapitant plus ondansetron vs. ondansetron monotherapy in the prevention of nausea and vomiting will be separately assessed, as measured by the respective CIN, CIV CR rates, among malignant glioma patients during RT and concomitant TMZ. The CR outcome for nausea will be defined as no use of rescue medication for nausea, while the CR outcome for vomiting will be defined as no use of rescue medication for vomiting. The CIN and CIV CR rates will be assessed via the modified MASCC Antiemesis Tool (MAT).

For each 3-week treatment regimen, compliance is defined as the percentage of days that pills were appropriately used. The distribution of compliance during treatment with ondansetron alone and with combination treatment will be described with a frequency distribution. A nonparametric paired test (e.g. Wilcoxon) may be used to compare compliance within the two regimens (as documented on the medication logs).

For the manuscript, adverse events that are possibly, probably, and definitely treatment related that are reported during the ~ 6 weeks of treatment will be summarized. For each type of adverse event experienced by a patient during rolapitant plus ondansetron and during ondansetron treatment, the maximum grade experienced by each patient will be tabulated by treatment group (i.e. rolapitant plus ondansetron or ondansetron treatment). Given the cross-over design of this study, patients will contribute data to both treatment groups. Two tabulations of toxicity data will be generated for review by the Safety Oversight Committee including one that includes all toxicities regardless of attribution, and another that includes only toxicities that are possibly, probably, and definitely related to protocol treatment. For each of these tabulations, the maximum grade of each type of toxicity experienced by each patient will be summarized with frequency distributions within each treatment (rolapitant plus ondansetron vs. ondansetron). For ClinicalTrials.gov, serious adverse events and other adverse events will be summarized separately. These tabulations will reflect the number of patients who experience each type of toxicity regardless of grade or attribution.

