9.2 Standard of Care Chemotherapy Treatment Plan

Temozolomide is an oral alkylating agent which has demonstrated anti-tumor activity as a single agent in the treatment of recurrent glioma. As stated previously, Stupp et al (2005) have demonstrated an increase in efficacy of temozolomide in combination with radiation therapy in the adjuvant treatment of primary malignant gliomas. In addition, the regimen was considered safe. Non-hematological grade 2 toxicities included: Fatigue (26%), other constitutional symptoms (7%), rash and dermatologic side effects (9%), infection (1%), vision (14%), and nausea and vomiting (13%). Grade 3 / 4 non-hematological toxicities occurred <10%: Fatigue (7%), other constitutional symptoms (2%), rash and dermatologic side effects (1%), infection (3%), vision (1%), and nausea and vomiting with a 5HT₃-RA (<1%). Thus, this safe and standard regimen will be utilized in this protocol. Daily temozolomide therapy will be calculated at a dose of 75 mg per square meter of

body surface area per day and be administered 7 days a week from the first until the last day of radiation therapy or a total of 42 days. Additional clinical and laboratory assessments will be at the discretion of the radiation therapist and oncologist.

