9.4 Anti-emetic Treatment

9.4.1 Antiemetic Treatment Plan

Sequence A involves administration of ondansetron alone for 3 weeks followed by the use of 1 dose of rolapitant plus daily doses of ondansetron for 3 weeks. Sequence B involves the use of 1 dose of rolapitant plus daily doses of ondansetron for 3 weeks followed by 3 weeks of ondansetron alone. For the rolapitant plus ondansetron weeks (1 or 4), patients will self-administer the single oral dose of rolapitant 1-2 hours before the first fraction of radiation on the planned week. Subjects will be given a prescription for ondansetron 8 mg pills to be taken 30 minutes before their daily TMZ dose. After the start of radiation therapy, the type of additional rescue antiemetic medication, if needed will be left up to the investigator's discretion. Subjects will be informed that they are allowed to take rescue antiemetic medication in either arm of the study. If the subject experiences nausea and vomiting and does take a rescue antiemetic, the subject will be asked to record the use of an additional antiemetic in the medication log provided to them. Subjects will complete weekly medication logs and surveys (see appendices) to capture study outcomes. Subjects will be told that the study is voluntary and that they may exit at any time if they wish.

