15.4.2 Statistical Hypothesis, Model, and Method of Analysis

As the primary analysis, a chi-square test will compare treatment regimens (ondansetron alone vs rolapitant + ondansetron) with respect to the proportion of patients who experience a CR during the first 2 weeks of RT and TMZ treatment. As an additional analysis, logistic regression will assess the effect of potential confounders on this relationship. Among the covariates that will be considered is the dose of decadron administered during the 2 weeks of RT and TMZ treatment.

As an exploratory analysis, a generalized linear model with a logit link that accounts for correlation between the CR status observed during the first and second treatment period within the same patient will be used to assess the impact of period, treatment, and their interaction. The purpose of this latter analysis is to assess whether the incremental effect of combination treatment relative to ondansetron alone is the same whether rolapitant is administered during the first period (i.e. first 3 weeks) or the second period (i.e. the second 3-week treatment regimen). It should be noted that this test will have low power to detect a clinically meaningful interaction effect. Within the context of the generalized linear model described above, the impact of covariates on CR rate will be explored. Included among these covariates will be the dose of decadron administer during that segment of the treatment regimen.

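### The TSQM-9 paired t-test and the optional compliance Wilcoxon have no period term, so any difference between weeks 1-3 and weeks 4-6 enters their error and, if completers are unequal, their estimate (minor)

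*Combined protocol and SAP*

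**What the plan says.** The design is a two-period, two-sequence cross-over. Section 9.4.1 gives the order in one sequence as "Sequence A involves administration of ondansetron alone for 3 weeks followed by the use of 1 dose of rolapitant plus daily doses of ondansetron", and sequence B reverses it. TSQM-9 is completed once per period, on days 22 and 43 (Table 7).

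For the TSQM-9 subscales, Section 15.5.2 sets one condition, "Assuming there is no evidence of a carry-over effect", and then "a paired t-test will be conducted comparing satisfaction with combination treatment and with ondansetron treatment alone". For compliance it plans a frequency distribution and adds: "A nonparametric paired test (e.g. Wilcoxon) may be used to compare compliance within the two regimens". Neither comparison has a period or sequence term.

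Elsewhere the plan does use the cross-over structure. In Section 15.4.2 an exploratory model for complete response (CR) "will be used to assess the impact of period, treatment, and their interaction". In Section 15.5.1, "Logistic regression will explore the potential that sequence influences patient preference".

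**The concern.** In this design each patient's combination-minus-ondansetron difference contains the regimen effect plus or minus the period effect, with the sign set by the sequence. A test that pools the sequences counts that systematic split as random noise. If the two sequences contribute different numbers of patients, part of the period effect also stays in the estimated regimen difference. Ruling out carry-over does not remove this, because a period effect needs no carry-over.

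A period effect is plausible on the protocol's own content. Section 9.3.3 moves from the initial target volume to a boost volume after 23-25 fractions. At five fractions a week the boost therefore starts late in week 5 or at the start of week 6, so only the second period includes it, and Section 12 lists treatment field among the predictors of nausea and vomiting. Section 15.4.2 also allows for decadron dose by treatment segment. None of this gives the size of an effect.

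At stake are the efficiency and, under imbalance, the unbiasedness of two secondary comparisons in a trial cut to 57 patients.

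**Working it through.** **Plan's own figures.** No power is stated for TSQM-9 or compliance. The nearest figure for patients who complete both regimens is the preference power in Section 15.7.1: 93% at n = 140, 65% vs 50%, two-sided 0.05. An exact binomial calculation gives 93.3%, so it reproduces.

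**Inputs from the documents.** 57 patients (Section 15.7.2); 1:1 permuted blocks (Section 9.6); 140 of 160 expected to complete both regimens (Section 15.7.1). Applied to the reduced target, completers are 57 × 140/160 ≈ 50.

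**Assumptions.** Within-sequence SD of the patient difference s = 1; true regimen effect tau = 0.4; period effect pi = 0, 0.25 or 0.5; completer splits 25/25, 22/28 and 28/22 (A/B).

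**Formulas.** Let d = combination minus ondansetron and pi = period 2 minus period 1. In sequence A the combination comes second, so the mean of d is tau + pi; in B it is tau - pi.
- Pooled mean: tau + pi(nA - nB)/N, so the bias is pi(nA - nB)/N.
- Variance seen by the paired test: about s² + 4·nA·nB·pi²/N², which is s² + pi² when balanced.
- Period-adjusted estimate: the average of the two sequence means. It has no bias, SE = (s/2)·√(1/nA + 1/nB), and N - 2 df.

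**Hand check, 25/25, pi = 0.5.** The paired test uses SE = √(1.25/50) = 0.158, although the true SE of the mean is √(1/50) = 0.141. With critical value 2.01, power ≈ Φ[(0.4 - 2.01 × 0.158)/0.141] = Φ(0.58) ≈ 72%. Because the SE is overstated, the test is conservative.

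**Hand check, unequal completers, pi = 0.5.** Bias = 0.5 × 6/50 = 0.06 in size. At 22/28 the mean falls to 0.34 and power ≈ Φ(0.16), about 57%. At 28/22 it rises to 0.46 and power ≈ Φ(1.01) ≈ 84%.

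**Simulation (two-sided 0.05):**

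| Completers A/B | pi (SD) | Power, paired | Power, adjusted | Bias, paired (SD) | Type I error, paired |
|---|---|---|---|---|---|
| 25/25 | 0 | 79% | 79% | 0 | 5.0% |
| 25/25 | 0.25 | 77% | 79% | 0 | 4.3% |
| 25/25 | 0.5 | 72% | 79% | 0 | 2.9% |
| 22/28 | 0.5 | 57% | 79% | -0.06 | 4.2% |
| 28/22 | 0.5 | 84% | 79% | +0.06 | 4.3% |

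The rank tests behave alike. With tau = 0.405 and 25/25, signed-rank versus period-adjusted rank power is 77% vs 78% at pi = 0.25 and 71% vs 79% at pi = 0.5.

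**Likelihood of imbalance.** If 28 and 29 are randomized and 7 drop out at random, a completer gap of 6 or more has probability of about 5%.

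**Compliance denominator.** Section 15.5.2 counts the percentage of days on which pills were appropriately used in each 3-week regimen. Section 9.2 has temozolomide "administered 7 days a week from the first until the last day of radiation therapy or a total of 42 days". Section 10.7.3 ties ondansetron to each chemotherapy dose and also lists days 1-42. Thirty fractions from a Monday end on day 5 × 7 + 5 = 40. Thirty-three, which Section 9.3.1 allows, end on day 6 × 7 + 3 = 45. The days on which a dose is due in the second period are therefore not settled.

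**The case against.** The strongest reply is that little hangs on these tests. The TSQM-9 objective is to describe the reasons behind preference, compliance is mainly a frequency distribution, the Wilcoxon is optional, and no power, alpha or decision is attached to either. The CR model that includes period is itself exploratory. The primary CR comparison uses the first two weeks only, and preference has its own sequence check. All of this stands, and it sets the severity.

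Three stronger readings are tempting, and the documents do not support them.

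- **That the paired tests simply lose power.** They do when completers are near balance and pi is not small. At pi = 0.25 SD and 25/25 the loss is only about 2 points. At 28/22 with pi = 0.5 SD the paired test rejects more often than the adjusted one, through bias rather than efficiency.
- **That a time trend will produce false positives.** A rejection rate near 7% under no effect needs a split such as 20/30 with pi = 0.5 SD. With about 28/29 randomized, 30 completers in one sequence is close to unreachable. At 22/28 there is no inflation.
- **That perfect ondansetron use scores 19/21 (90.5%) in the second period.** This holds only if dosing stops on day 40 and the denominator stays at 21. Sections 9.2 and 10.7.3 and Table 7 also give 42 days, and Section 15.5.2 fixes no denominator and may already permit counting only due days.

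**Conclusion.** The omission is real: nothing in the plan adds a period term to the TSQM-9 or compliance comparison, and the carry-over condition is a different safeguard. Its effect depends wholly on a period difference that the documents do not quantify. Over the assumed range of 0 to 0.5 SD, balanced completers cost 0 to about 7 points of power, with a conservative test. Mild imbalance adds a bias of up to 0.06 SD whose direction cannot be known in advance. With no period effect there is no harm. Severity is minor.

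**What to change.** In Section 15.5.2:

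1. Replace the paired t-test with a two-sample t-test comparing within-patient period differences (period 1 minus period 2) between sequences A and B. Half the difference between the sequence means estimates the regimen effect. A model with regimen and period is equivalent.
2. If compliance is tested, use a rank-sum test on the same differences.
3. State that the compliance denominator is the days on which a dose was due. Reconcile Sections 9.2 and 10.7.3 and Table 7 on whether temozolomide and ondansetron end with the last fraction or on day 42.

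The cost is wording and one degree of freedom; no new data are needed. If there is no period effect, the power lost is nil at 25/25, under 1 point at 22/28, and about 2 points even at 20/30. The change does not deal with carry-over, so the existing condition should stay.

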5 PROTOCOL SYNOPSIS AND RESEARCH SUMMARY

5.1 Purpose

The purpose of this two-arm randomized phase 2 study is to assess the efficacy and patient satisfaction of oral rolapitant plus ondansetron vs. oral ondansetron *monotherapy* in malignant glioma (MG) patients receiving six weeks of standard cranial radiation therapy (RT) and concomitant temozolomide (TMZ).

Primary Objective:

Compare the efficacy of rolapitant plus ondansetron vs. ondansetron mono therapy in the prevention
of chemoradiation-induced nausea and vomiting (chemo-RINV), as measured by the overall complete
response (CR) rate (where CR is defined as no emesis, no rescue antiemetic), among malignant glioma
patients during the standard ~ 6 weeks of RT and concomitant multi-dose TMZ

Secondary Objectives:

- KEY secondary objective: Assess whether malignant glioma patients receiving RT and concomitant TMZ
 are more satisfied with rolapitant plus ondansetron vs. ondansetron monotherapy for the prevention of
 chemo-RINV
- 2. Describe the rationale behind a patient's satisfaction with antiemetic preference based upon effectiveness, convenience and global satisfaction
- 3. Compare the efficacy of rolapitant plus ondansetron vs. ondansetron monotherapy in the prevention of nausea and vomiting separately, as measured by the respective CIN, CIV -CR rates, among malignant glioma patients during RT and concomitant TMZ
- 4. Evaluate compliance of rolapitant plus ondansetron vs. ondansetron monotherapy
- 5. Assess the safety of rolapitant plus ondansetron vs. ondansetron monotherapy in the prevention of RINV in glioma patients receiving RT and concomitant TMZ

Hypotheses

1. This is a hypothesis-testing protocol. Hypothesis: rolapitant plus ondansetron will produce an equally or a more effective RINV CR rate when compared to ondansetron monotherapy in glioma patients receiving RT and concomitant TMZ.

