8 OBJECTIVES AND ENDPOINTS

| | Objective | Endpoint | Analysis |
|------------------|--|--|--------------------|
| Primary | Compare the efficacy of rolapitant plus ondansetron vs. ondansetron monotherapy in the prevention of nausea and vomiting, as measured by the overall complete response (CR) rate, among malignant glioma patients during RT and concomitant TMZ | Complete response (CR) rate associated with rolapitant plus ondansetron and ondansetron alone during the first two weeks of RT and concomitant TMZ. The CR rate is defined as the proportion of patients with no emetic episode or use of rescue medication while receiving radiation and concomitant TMZ. The CR rate will be assessed via the modified MASCC Antiemesis Tool (MAT) within daily diary. ¹⁷ | See section 15.4 |
| KEY Secondary | Assess whether malignant glioma patients receiving RT and concomitant TMZ are more satisfied with rolapitant plus ondansetron vs. ondansetron monotherapy for the prevention of RINV | The percentage of patients who prefer rolapitant plus ondansetron over ondansetron alone, as determined by response to the question with "Which nausea medication regimen was I most satisfied with?" | See section 15.5.1 |
| Secondary | Describe the rationale behind a patient's satisfaction with antiemetic preference based upon effectiveness, convenience & global satisfaction | Mean patient satisfaction scores during weeks 3 and 6 for effectiveness, convenience, and global satisfaction for ondansetron pill and rolapitant plus ondansetron using the 9-item TSQM-9 patient satisfaction survey. ¹⁶ Three subscales are computed: effectiveness (3 items), convenience (3 items), and global satisfaction (3 items). | See section 15.5.2 |
| Secondary | Compare the efficacy of rolapitant plus ondansetron vs. ondansetron monotherapy in the prevention of nausea and vomiting separately, as measured by the respective CIN, CIV -CR rates, among malignant glioma patients during RT and concomitant TMZ | The CR outcomes for nausea will be defined in comparable terms (no use of rescue medication for nausea). The CR outcome for vomiting will be defined in comparable terms (no use of rescue medication for vomiting). The CIN, CIV CR rate will be assessed via the modified MASCC Antiemesis Tool (MAT) within daily diary. | See section 15.5.2 |

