15.4.1 Variable

Complete response (CR) rate associated with rolapitant plus ondansetron and that associated with ondansetron during the first two weeks of RT and concomitant TMZ is defined as the proportion of patients with no emetic episode or use of rescue medication while receiving radiation and concomitant TMZ. The CR rate will be assessed via the modified MASCC Antiemesis Tool (MAT).¹⁷

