15.7 Sample Size Calculation

15.7.1 Original Study Design

One hundred seventy (170) glioma patients will be enrolled with the expectation that 160 patients will be randomized to receive one of two treatment sequences of anti-emetic therapy for the prevention of nausea and vomiting associated with RT and concomitant TMZ. A permutated block randomization with an allocation ratio of 1:1 will be used to assign patients to sequence A or B. Sequence A involves a 3-week regimen of daily ondansetron followed by a 3-week regimen consisting of rolapitant (day 22 only) and daily ondansetron; whereas Sequence B involves a 3-week regimen of rolapitant (day 1 only) and daily ondansetron followed by a 3-week regimen of daily ondansetron. The study has one primary and one KEY secondary endpoint: CR rate and patient overall preference for ondansetron treatment with or without rolapitant. Though the primary CR rate endpoint will focus on treatment during the first 2 weeks of RT and TMZ, a crossover design is proposed so that a patient will experience both modes of treatment, and be equipped to make a comparative assessment of preference.

Power Calculations for Complete Response, Primary Endpoint: The power of the comparison of ondansetron and the combination of ondansetron and rolapitant relative to the CR rate during the initial 2 weeks of treatment with RT and TMZ will be considered here. This comparison will focus on the anti-emetic experience during the first regimen of the two treatment regimens that the patient will receive. Let

p₁ = overall complete response rate for the first 2 weeks of treatment with the combination antiemetic regimen, and

 p_0 = overall complete response rate during the first 2 weeks of treatment with ondansetron alone.

The hypothesis that will be assessed is whether the CR rate with combination treatment is greater than that with ondansetron alone. Specifically, the hypothesis that will be tested is as follows:

 H_0 : $p_1 \le p_0$ versus H1: $p_1 > p_0$

Temozolomide prescribing information reports a vomiting rate of 20% with concomitant RT + TMZ. Anti-emetic treatment failure includes the occurrence of vomiting or the use of an anti-emetic for nausea and/or vomiting. Therefore, we anticipate that approximately 25% of patients receiving ondansetron alone to either vomit or receive an anti-emetic. Equivalently, a CR rate of 75% is anticipated with ondansetron alone.

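### The separate nausea and vomiting complete responses are defined by rescue use alone, so a patient who vomits without taking rescue counts as a vomiting complete responder

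*Combined protocol and SAP*

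**What the plan says.** One secondary objective is to compare the two regimens on nausea and on vomiting as separate outcomes. Section 15.5.2 says efficacy "in the prevention of nausea and vomiting will be separately assessed, as measured by the respective CIN, CIV CR rates". It then gives the rule: "the CR outcome for vomiting will be defined as no use of rescue medication for vomiting". The nausea rule has the same form. The endpoint column of Section 8 reads "The CR outcomes for nausea will be defined in comparable terms (no use of rescue medication for nausea") and "The CR outcome for vomiting will be defined in comparable terms (no use of rescue medication for vomiting"). Both sections name the modified MAT as the assessment tool. No other section defines these two rates; Section 5.1 only names them.

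The primary CR is built differently. Section 5.1 gives it as one "where CR is defined as no emesis, no rescue antiemetic", and Section 15.4.1 as the "proportion of patients with no emetic episode or use of rescue medication while receiving radiation and concomitant TMZ". The sample size section agrees: "Anti-emetic treatment failure includes the occurrence of vomiting or the use of an anti-emetic for nausea and/or vomiting".

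Section 9.4.1 allows rescue in either arm but does not require it. Section 9.6 makes the assignment unblinded.

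**The concern.** The objective concerns prevention of a symptom, but the stated rule records only whether a drug was taken for it. A patient who vomits and takes no rescue is a complete responder for vomiting. The same patient fails the primary CR and meets the failure definition in Section 15.7.1.

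For nausea there is no such conflict, because the primary CR contains no nausea symptom; nausea enters it only through rescue. There the point rests on the objective alone: a rescue-only rule does not show whether nausea was prevented.

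The nausea CR is the only efficacy endpoint aimed at nausea, so under the stated rule the occurrence of nausea would not be counted in any efficacy endpoint. Patients also decide on rescue knowing which regimen they are on, so a difference in rescue habits between regimens would pass straight into these rates.

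**Working it through.** The plan gives no expected rate, power or sample size for the separate nausea and vomiting CR, so there is no stated figure to reproduce. The check is a comparison of definitions, then an illustration for vomiting.

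**Definitions applied to one patient who vomits and takes no rescue**

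- Primary CR (Sections 5.1 and 15.4.1): not a responder, because of the emesis.
- Failure definition in Section 15.7.1: failure, because of the vomiting.
- Vomiting CR (Sections 8 and 15.5.2): responder, because no rescue was taken for vomiting.
- Nausea CR (Sections 8 and 15.5.2): responder, because no rescue was taken for nausea.

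**Inputs for the illustration**

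- Vomiting rate on ondansetron alone, v0 = 0.20. Section 15.7.1: "Temozolomide prescribing information reports a vomiting rate of 20% with concomitant RT + TMZ". No two-week window is stated for it.
- 57 patients (Section 15.7.2) allocated 1:1 (Section 9.6), so 57/2 = 28.5 receive ondansetron alone first.
- u, the share of vomiting patients who take no rescue: assumed, from 0 to 1.
- Rescue for vomiting is assumed to be taken only by patients who vomit. Without this assumption, the CR rates below are upper limits.

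**Level of the rate**

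Vomiting CR as written = 1 − v0 × (1 − u). Vomiting CR with a no-emesis condition = 1 − v0 = 0.80. Patients counted as responders despite vomiting = n × v0 × u.

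| u | As written | With no-emesis condition | Of 28.5 (first period) | Of 57 (both periods pooled) |
|---|---|---|---|---|
| 0 | 80% | 80% | 0 | 0 |
| 0.25 | 85% | 80% | 1.4 | 2.9 |
| 0.50 | 90% | 80% | 2.9 | 5.7 |
| 0.75 | 95% | 80% | 4.3 | 8.6 |
| 1 | 100% | 80% | 5.7 | 11.4 |

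The last two columns differ because Section 15.5.2 does not say which period or window these endpoints cover. If only the first regimen counts, the denominator is about 28. If every patient contributes an ondansetron-alone period, it is up to 57.

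With the 26% vomiting rate from the Korean cohort cited in Section 5.2, the as-written rate runs through 74%, 80.5%, 87%, 93.5% and 100% over the same values of u, against 74% with the no-emesis condition.

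**Difference between regimens**

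Let v be the vomiting rate and r = 1 − u the share of vomiting patients who take rescue, with 0 for ondansetron alone and 1 for the combination. The true difference is v0 − v1. The difference as written is v0 × r0 − v1 × r1. If r0 = r1 = r, it equals r × (v0 − v1), so it shrinks by the common rescue share.

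With v0 = 0.20 and an assumed v1 = 0.10, the true difference is 10 points:

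- r0 = r1 = 0.5: 0.20 × 0.5 − 0.10 × 0.5 = 0.05, or 5 points.
- r0 = 0.75, r1 = 0.25: 0.150 − 0.025 = 0.125, or 12.5 points.
- r0 = 0.25, r1 = 0.75: 0.050 − 0.075 = −0.025, or −2.5 points.

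These cases show that the difference can shrink, grow or reverse. They do not say which is likely.

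**The case against.** The strongest reply is that the definitions are shorthand. Section 8 introduces them as comparable in form, directly after a primary CR that requires no emesis as well as no rescue. Both sections name the MAT, which Section 12.7.3 describes as measuring vomiting and acute and delayed nausea, and a rescue-only endpoint would leave its symptom items with no role. The modified MAT and the logs are attached but not shown, so a scoring rule there cannot be excluded. This makes incomplete wording the likely explanation. It does not remove the problem: the brackets in Section 8 mention rescue only, and Section 15.5.2 drops the language of comparability and states the rule outright. An analyst following Section 15.5.2 would program rescue use alone.

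Second, the endpoint carries limited weight. It has no stated test or power, and the opening list of secondary objectives in Section 15.5 omits it. That is fair, and it limits the consequence. If the MAT is completed as planned, the symptom data will exist either way.

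Third, the sizes rest on assumed rescue shares and an assumed vomiting rate for the combination. This also stands: the figures show what the rule permits, not what will happen.

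**Conclusion.** The concern holds. Followed as stated, the rule counts vomiting without rescue as complete response for vomiting and makes both separate rates measures of rescue use rather than of prevention. For vomiting at the planning rate of 20%, the overstatement is 20 × u percentage points: none if every vomiting patient takes rescue for it, 20 points if none does. This assumes that only patients who vomit take rescue for vomiting. The effect on the comparison between regimens is unknown in size and direction, because the documents give neither rescue shares nor a vomiting rate for the combination. They support no figure for nausea. The primary CR and the preference endpoint are not affected. This should be fixed before analysis.

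**What to change.** Amend Sections 8 and 15.5.2 together:

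- Vomiting CR: no emetic episode on the MAT and no rescue taken for vomiting.
- Nausea CR: no nausea on the MAT, at a threshold the study team fixes before analysis, and no rescue taken for nausea.
- State the window and treatment period for both, which Section 15.5.2 leaves open.

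Do not count any rescue as failure for both outcomes. Over the same window that would make the vomiting CR identical to the primary CR.

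The definitions need the reason for each rescue dose. Section 9.4.3 mentions only dates, and the logs are not shown, so whether the reason is recorded cannot be checked. If it is not, report no emesis and no nausea from the MAT as the two outcomes, with rescue use beside them. The dose range-finding study described in Section 7.2.2 lists both as endpoints distinct from CR. Under this fallback, a patient who takes rescue and does not vomit counts as no emesis. Section 9.4.2 also lets rescue medication make up a missed dose, so the rescue figures may include doses taken without symptoms.

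The cost is a wording change in two sections. The MAT is already administered, so new data collection is unlikely. The reported rates may be lower, and a primary responder with nausea can fail the nausea CR. The nausea threshold is a new choice made late in an unblinded trial: Section 15.4 reports 53 patients randomized by mid-January 2022 against a target of 57. It should therefore be recorded with a date before outcomes are examined by regimen.
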